### **Comparing NGENUITY vs conventional microscope in a new Hydrus user**

**Design:** Prospective, masked study involving two new glaucoma Fellows learning to implant the Hydrus stent with supervision by single Attending. The fellows will alternate performing the surgeries (N=32) utilizing NGENUITY vs Zeiss Lumera conventional microscope.

**Hypothesis:** Hydrus cases using the NGENUITY will take less time, have fewer misdirected attempts, safer outcomes, and superior teaching value due to its better visualization of angle anatomy (higher resolution, improved depth of focus)

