#### **Key Endpoints:**

**Primary:** Total Hydrus time (time of cannula in /out), # of attempts (piercing TM)

**Secondary:** Other efficiency & efficacy endpoints: # of attempts entering reentering AC, # of times readjusting focus/microscope, rate of intraoperative adverse events, posture, and previously utilized Fellow and Attending questionnaire

**Exploratory:** Safety outcomes at POD#1 and POM#1

**Statistical Considerations:** N= 32, descriptive qualitative stats

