Comparing NGENUITY vs Conventional Microscope in a New Hydrus User

Statistical Analysis Plan

NCT05529966

March 14, 2025

The original planned sample size for this study was 32 participants, with each participant enrolling a single study eye. However, it was later determined that if both eyes of a participant were eligible for the study, the same participant could be enrolled for their second eye surgery, resulting in a revised planned sample size of a total of 32 eyes. Additionally, the study protocol was modified to include a total of three glaucoma fellows participating in the surgeries, rather than the originally planned two. To analyze the outcome measures, a two-tailed t-test with two-sample unequal variance was used for primary and secondary outcomes with both NGENUITY and convention microscope groups. After Bonferroni correction, the new threshold for statistical significance was <0.002083333.

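### One Bonferroni threshold covers primary and secondary outcomes alike, a conservative choice that costs the two primary endpoints much of their power (minor)

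*SAP*

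**What the plan says.** The protocol, under Key Endpoints, ranks its outcomes. Two are primary: "Total Hydrus time (time of cannula in /out), # of attempts (piercing TM"). The secondary list has five headings: the number "of attempts entering reentering AC, # of times readjusting focus/microscope, rate of intraoperative adverse events, posture, and previously utilized Fellow and Attending questionnaire". Its statistical plan is "N= 32, descriptive qualitative stats", with no alpha, effect size, SD or power.

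The SAP is a single paragraph. It reports that "a two-tailed t-test with two-sample unequal variance was used for primary and secondary outcomes", and then: "After Bonferroni correction, the new threshold for statistical significance was <0.002083333". It gives no separate level for the primaries and no testing order. It does not give the alpha before correction or the tests counted. It also records that "if both eyes of a participant were eligible for the study, the same participant could be enrolled for their second eye surgery", and that the study was changed to "include a total of three glaucoma fellows participating in the surgeries". It describes no adjustment for either.

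**The concern.** A primary endpoint is normally named so that it can be tested with most or all of the available alpha. Here the ranking plays no part in the decision rule: total Hydrus time must meet the same cut-off as any single lower-ranked comparison. With only 32 eyes, so strict a cut-off could turn a large, real difference on a primary into a non-significant result. A procedure that uses the ranking can control the same family-wise error and leave the primaries far better powered.

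**Working it through.** **1. The stated threshold.** 0.05/24 = 0.00208333 and 0.025/12 = 0.00208333, so both reproduce it. The protocol lists 2 + 5 = 7 headings, or 8 if the Fellow and Attending questionnaires are counted separately. These give 0.05/7 = 0.00714 and 0.05/8 = 0.00625, which do not match. Individual questionnaire items could make up the difference.

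**2. Share of alpha left to the primaries.** 2 × 0.0020833 = 0.0042. That is 8% of 0.05, or 17% of 0.025. A two-endpoint primary family would allow 0.05/2 = 0.025 each, 12 times the stated level, or 0.025/2 = 0.0125 each, 6 times.

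**3. Power for one primary.** The documents give no effect size, SD or allocation ratio. Assumed: 16 vs 16 independent eyes, equal SDs, roughly normal outcomes. The smallest observed difference that can be significant is t(1 − α/2; 30 df) × √(2/16). Power comes from the noncentral t with 30 df and noncentrality d × √(16/2).

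| | α = 0.025 | α = 0.0125 | α = 0.0020833 |
|---|---|---|---|
| Smallest significant observed difference (SD) | 0.83 | 0.94 | 1.19 |
| Power at 0.5 SD | 0.188 | 0.124 | 0.038 |
| Power at 0.8 SD | 0.471 | 0.362 | 0.161 |
| Power at 1.0 SD | 0.680 | 0.573 | 0.319 |
| Power at 1.2 SD | 0.843 | 0.764 | 0.520 |
| Power at 1.5 SD | 0.966 | 0.936 | 0.796 |
| Difference detectable with 80% power (SD) | 1.14 | 1.25 | 1.51 |

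The gap between the outer columns is widest near 1.0 SD, at 36 points. A 20 vs 12 split gives 0.649, 0.539 and 0.290 at 1.0 SD. Attempts is a count. With 1 + Poisson attempts (assumed) and mean extra attempts of 1.5 vs 0.5 (1.0 SD), Welch power is 0.687 at 0.025 and 0.274 at 0.0020833.

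**4. Alternatives that keep the family-wise level.** Simulated with both primaries at 1.0 SD and correlation 0 to 0.3 between outcomes; power for one primary:
- Bonferroni over 24: 0.31.
- Holm over the same tests: 0.31 if the other effects are null, rising to 0.37–0.40 if all are 1.0 SD (up to 0.39 for 12 tests from 0.025).
- Holm over the two primaries at 0.05: 0.74–0.75, with both rejected in 0.60–0.63 of trials. At 0.025: 0.62–0.63.

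Relaxing the primaries without a gate does not keep the level: 2 × 0.025 + 22 × 0.0020833 = 0.0958.

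**5. Cost of the gate (starting alpha 0.05).** With both primaries at 1.0 SD, secondaries cannot be tested in 1 − 0.63 = 0.37 to 1 − 0.60 = 0.40 of trials. If all 24 outcomes have a 1.0 SD effect, power for one secondary goes from 0.318 to 0.235 at correlation 0 and stays at 0.312 at correlation 0.3. With primaries at 0.5 SD and secondaries at 1.5 SD, it falls from about 0.79 to 0.07–0.10.

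**6. Are the eye-level p-values valid?** The documents do not say how second eyes fall. Simulated Welch error with within-person correlation 0.3–0.5 (assumed):
- 4 or 8 participants per arm with both eyes in the same arm: 0.0037–0.0116 at nominal 0.0020833, and 0.036–0.069 at nominal 0.025.
- 8 or 16 participants with one eye in each arm: 0.00004–0.0009 and 0.0025–0.015.

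In the same-arm case the sum over 24 tests is 24 × 0.0037 = 0.089 to 24 × 0.0116 = 0.278, so the Bonferroni bound of 0.05 is no longer guaranteed. In the split case it is more than met. Fellow effects were not simulated.

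**The case against.** The strongest defence is that one family is a legitimate choice. The protocol's hypothesis is that "Hydrus cases using the NGENUITY will take less time, have fewer misdirected attempts, safer outcomes, and superior teaching value", so safety and teaching value are claims in their own right. Plain Bonferroni over one unranked family requires exactly this kind of threshold, and it lets any secondary be claimed whatever happens to the primaries. A primary label makes a separate family reasonable but does not oblige it. This stands: a reader might call the threshold needlessly strict, but the strictness buys those secondary claims, as step 5 shows.

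The power loss also rests on assumed effects. It is large only for differences of about 0.8 to 1.5 SD; moderate effects are mostly missed under either rule. No stated power target is defeated. And the SAP is in the past tense, so the analysis may already be done, in which case a new decision rule would carry little confirmatory weight.

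Three stronger readings are tempting and are not supported:
- That the correction is wrong because 24 exceeds the seven or eight listed items. Questionnaire items may account for the rest, and the starting alpha is unknown. The count is undocumented, not shown to be wrong.
- That the rule is invalid. The error could lie on either side of nominal, depending on how second eyes fall.
- That the rule is simply valid. That needs sound p-values and a family fixed in advance, and the documents establish neither.

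What the defence does not answer is that Holm over the same tests has the same error control and is never less powerful.

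**Conclusion.** The point holds as a minor one about power and reporting. The SAP's single threshold gives the protocol's endpoint ranking no role. Under the stated assumptions a true 1.0 SD difference on one primary would be detected about 32% of the time, against 68% at 0.025, or 57% at 0.0125 if the starting alpha is 0.025. The rule is conservative by design and creates no type I error fault of its own. Whether it delivers its nominal family-wise level depends on eye-level p-values whose validity is open. The figures assume 16 vs 16 independent eyes, equal SDs and near-normal outcomes. A reader might also infer that a real primary effect has been missed; the documents report no results and cannot support that.

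**What to change.** 1. **In every case:** state the starting alpha, list the tests counted, and say when the list was fixed. This costs only wording, and the level available to the primaries depends on the answer.
2. **At minimum, if results have not been seen:** replace Bonferroni with Holm over the same tests. The gain for a primary ranges from almost nothing to about 8 or 9 points at 1.0 SD, with no loss of error control.
3. **Fuller change, only if results have not been seen:** test the two primaries as their own Holm family at the starting alpha. At 0.05 this means the smaller p against 0.025 and the other against 0.05; both are halved if the starting alpha is 0.025. Then either test the secondaries with Holm only after both primaries are rejected, or report them as estimates with confidence intervals. The price is that no secondary, including teaching value, can be claimed if a primary fails: about 40% of trials with both primaries at 1.0 SD, and far more if the primary effects are moderate.
4. **Pair the relaxed level with an analysis that accounts for participant and fellow.** This also costs some power. With 4 or 8 participants giving both eyes to one arm (assumed correlation 0.3–0.8), averaging their two eyes gives 54–63% at 0.025 and 19–26% at the present threshold, for 1.0 SD. Averaging alone does not deal with fellow.
5. **If results have been seen:** keep 0.002083333 as the reported rule and show Holm over the same tests and the primary-only family beside it, labelled post hoc.

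None of this needs new data; it takes SAP wording and a re-run of the tests.

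### On its plain reading, the SAP tests the intraoperative adverse-event rate at p < 0.00208 with 32 eyes; a non-significant result there says almost nothing about safety, so harms should be described with intervals

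*SAP*

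**What the plan says.** The protocol's Hypothesis names safety as one of NGENUITY's expected advantages: "Hydrus cases using the NGENUITY will take less time, have fewer misdirected attempts, safer outcomes". Under Key Endpoints, the secondary list includes the "rate of intraoperative adverse events", while "Safety outcomes at POD#1 and POM#1" are exploratory. The Statistical Considerations line in the same section gives N = 32 and asks only for descriptive statistics.

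The SAP goes further: "a two-tailed t-test with two-sample unequal variance was used for primary and secondary outcomes". It then gives one threshold: "After Bonferroni correction, the new threshold for statistical significance was <0.002083333". It makes no exception for safety endpoints, does not list the tests counted in the correction, and plans no confidence interval for any outcome. The total is 32 eyes, and both eyes of a participant may be enrolled.

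**The concern.** The intraoperative adverse-event rate is secondary, so the SAP's test sentence covers it, and the only threshold that the SAP gives is the corrected one. It is the one safety endpoint with a planned test. Bonferroni correction limits false positive claims and pays for this with more missed differences. In a comparison of harms, a miss can be the costlier error, above all if the excess lies with NGENUITY, the device expected to be safer.

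At stake is how the safety result will be read. With sparse yes/no events in 32 eyes, a large observed imbalance could be reported as not significant. Without an interval beside it, the reader cannot tell that result from evidence of similar safety.

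**Working it through.** **Inputs from the documents.** Threshold 0.002083333, two-tailed unequal-variance (Welch) t-test and 32 eyes (SAP). Adverse-event rate as a secondary endpoint (protocol, Key Endpoints).

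**Assumptions.** 16 eyes per arm (no per-arm number is stated), at most one yes/no event per eye, and independent eyes. The documents give no event rate, so the rates below are illustrative.

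**1. The SAP's own figure.** 0.05/24 = 0.00208333, which matches. The 0.05 and the 24 are back-calculated: 0.025/12 and 0.10/48 give the same value.

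**2. Zero events against seven.** Code each eye 0 or 1.
- Difference: 7/16 − 0/16 = 0.4375.
- Sample variance in the seven-event arm: (7/16)(9/16)(16/15) = 0.2625. In the other arm it is 0.
- Standard error: √(0.2625/16) = 0.1281.
- t = 0.4375/0.1281 = 3.416. With zero variance in one arm, the Welch degrees of freedom are 16 − 1 = 15.
- Two-sided p = 0.0038, above 0.00208.

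**3. Where the threshold is crossed (zero events in the other arm, 16 per arm).**

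| Events in second arm | Welch p | Fisher exact p |
|---|---|---|
| 6/16 | 0.0090 | 0.0177 |
| 7/16 | 0.0038 | 0.0068 |
| 8/16 | 0.0015 | 0.0024 |
| 9/16 | 0.0005 | 0.0008 |

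Against zero events, 7 is the largest count that stays non-significant under the SAP's test.

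**4. Other splits of 32.** Welch p for 0 against 7 events, zero-event arm first: 14:18, 0.0043; 15:17, 0.0041; 17:15, 0.0035; 18:14, 0.0032. All are above the threshold.

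**5. Chance of flagging a true difference.** For each pair of counts (i, j) from 0 to 16, multiply the two binomial probabilities, Bin(i; 16, p₁) × Bin(j; 16, p₂), and sum over the pairs whose p-value is below the threshold.

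| True rates | Welch, 0.00208 | Welch, 0.05 | Fisher, 0.05 |
|---|---|---|---|
| 5% v 25% | 1.5% | 34% | 19% |
| 10% v 40% | 11% | 50% | 36% |
| 0% v 43.75% | 40% | 96% | 90% |

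**6. What an interval would show.** For 0/16 the two-sided 95% exact upper limit is 1 − 0.025^(1/16) = 20.6%. An arm with no events is still compatible with a true rate of about one in five.

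**The case against.** **The safety claim is a benefit claim.** The protocol lists safety beside speed and fewer attempts as an advantage of NGENUITY, so correcting for multiplicity in the favourable direction is defensible. This stands. The argument that correction works against detecting harm applies only to an excess of events with NGENUITY.

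**Sample size is also a bottleneck.** Even at 0.05 the chance of flagging is 34% or 50% in the two moderate scenarios (19% or 36% with Fisher's test). This stands too: lifting the correction would not make safety testable. But it argues for description with intervals, not for keeping the threshold.

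**Membership of the corrected family is inferred.** The SAP does not list the tests. The inference rests on the endpoint's secondary status and the SAP's general sentence. If adverse events were left out, the SAP should say so.

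**Stronger readings to avoid.** A reader might infer that a safety difference is almost impossible to flag. That fits moderate differences, but at true rates of 0% and 43.75% the planned test flags about 40% of the time. A reader might also infer that the plan has no usable safety analysis at all. But the day-1 and month-1 outcomes are exploratory, so the SAP's test sentence does not cover them, and the protocol already asks for descriptive statistics. Nor do the documents plan an equivalence claim; the misreading is a risk for the report, not a stated intention.

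**Conclusion.** The concern holds in a limited form. On the plain reading of the protocol's endpoint list and the SAP, intraoperative adverse events are judged by a Welch t-test at 0.00208. Under the stated assumptions, an observed contrast of 0% against 44% would be labelled not significant. For true rates of 5% and 25%, the correction takes the chance of a flag from 34% to 1.5%. A non-significant result therefore neither refutes the safety part of the hypothesis nor supports similar safety.

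The non-significance of 0 against 7 holds for every split checked from 14:18 to 18:14. The flagging chances depend on the assumed rates and on 16 per arm. Second eyes of the same participant would make the independence assumption only approximate. The time and attempt endpoints are not affected by this point. It concerns how harms are reported, and it can be put right at almost no cost.

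**What to change.** - Take intraoperative adverse events out of the thresholded comparisons. Report them with the day-1 and month-1 safety outcomes, as counts per arm with exact 95% confidence intervals and a risk difference with its confidence interval. This agrees with the descriptive approach in the protocol's Statistical Considerations.
- State that a non-significant or small difference is not evidence of similar safety.
- State that the safety part of the hypothesis was described and not formally tested. Leave the hypothesis text as it stands; rewriting it is not needed.
- List the tests that make up the Bonferroni correction, so that the family is explicit.

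**Cost.** SAP and report wording, with no new data. The sponsor gives up a formal claim of safety superiority. The SAP is written in the past tense, so the analysis may already be done. If it is, the change must be labelled post hoc and the tests as originally planned should still be disclosed.

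### The single-step Bonferroni threshold is valid, but Holm's step-down on the same tests has the same family-wise error bound and never rejects fewer

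*SAP*

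**What the plan says.** The SAP is a single paragraph. It states that "a two-tailed t-test with two-sample unequal variance was used for primary and secondary outcomes", comparing the two microscope groups, and then gives one rule for significance: "After Bonferroni correction, the new threshold for statistical significance was <0.002083333". It names neither the family-wise alpha nor the number of tests. It describes no step-down procedure, testing order or separate family for the primary endpoints.

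The protocol supplies no other rule. Under Key Endpoints it lists two primary endpoints, "Total Hydrus time (time of cannula in /out), # of attempts (piercing TM"), followed by a set of secondary endpoints. Its statistical section reads only "N= 32, descriptive qualitative stats". The SAP restates the sample size as "resulting in a revised planned sample size of a total of 32 eyes".

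**The concern.** Under single-step Bonferroni every test meets the same fixed threshold, however many of the others have succeeded. Once a hypothesis has been rejected, its share of alpha is no longer needed to protect the remaining tests, but the single-step rule does not pass it on. Holm's procedure does, and it needs no further assumption.

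This matters most when several outcomes are expected to move together. The protocol's hypothesis is of that kind: it predicts an advantage for NGENUITY in time, misdirected attempts, safety and teaching value. With 32 eyes and a cut-off near 0.002, some outcomes that truly differ could be declared non-significant under Bonferroni and significant under Holm, with the family-wise error guaranteed at the same level.

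The point takes the SAP's family of tests as given. Which outcomes belong in it, and whether the primaries should share it with the secondaries, are separate questions.

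**Working it through.** **Inputs from the documents.** Threshold 0.002083333, Bonferroni, two-tailed unequal-variance (Welch) t-tests, primary and secondary outcomes together (SAP); 32 eyes (SAP).

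**Assumptions.** The documents do not give these: family-wise alpha 0.05; 16 eyes per arm, all independent; normal outcomes with pairwise correlation 0.3; real effects of 1.2 or 1.5 SD.

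**Step 1: reproduce the SAP's figure.** Bonferroni is alpha/m. With alpha = 0.05, 0.05/0.002083333 = 24.0, so m = 24 and 0.05/24 = 0.00208333, as stated. An alpha of 0.025 would imply 12 tests and 0.10 would imply 48; 0.01 gives 4.8, which is not a whole number. The Šidák value, 1 − 0.95^(1/24) = 0.002135, does not match, so the figure is plain Bonferroni. The argument below holds for any alpha and m.

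**Step 2: Holm's thresholds.** The k-th smallest p-value is compared with 0.05/(24 − k + 1), and testing stops at the first failure.

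| Rank k | Holm threshold | Bonferroni |
|---|---|---|
| 1 | 0.05/24 = 0.002083 | 0.002083 |
| 2 | 0.05/23 = 0.002174 | 0.002083 |
| 6 | 0.05/19 = 0.002632 | 0.002083 |
| 12 | 0.05/13 = 0.003846 | 0.002083 |
| 18 | 0.05/7 = 0.007143 | 0.002083 |
| 24 | 0.05/1 = 0.05 | 0.002083 |

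**Step 3: why Holm never rejects fewer.** If a p-value is at or below alpha/m, so is every smaller one. All of them therefore pass their Holm thresholds, each of which is at least alpha/m.

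**Step 4: why the bound is the same.** Suppose m0 of the m null hypotheses are true. When the first true null is reached, at most m − m0 hypotheses have been rejected, so its threshold is at most alpha/m0. The chance that any of the m0 true nulls has a p-value that small is at most m0 × alpha/m0 = alpha, under any dependence.

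**Step 5: size of the gain.** Simulation of 24 Welch tests under the assumptions above, with effects of 1.2 SD. The rows for 2, 6, 12 and 24 real effects use 20,000 replicates; the row for 20 uses 6,000.

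| Real effects (of 24) | Average power per real effect, Bonferroni | Holm | Gain (points) | Realised family-wise error, Bonferroni / Holm |
|---|---|---|---|---|
| 2 | 51.8% | 52.1% | 0.3 | 0.040 / 0.042 |
| 6 | 51.1% | 52.9% | 1.8 | 0.034 / 0.039 |
| 12 | 51.1% | 55.3% | 4.2 | 0.021 / 0.030 |
| 20 | 51% | 61% | about 10 | both below 0.05 |
| 24 | 51.1% | 66.0% | 14.9 | no true nulls |

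At 1.5 SD the gain is 78.9% to 83.3% with 12 real effects and 79.3% to 93.5% with 24. With no real effects the two methods have the same family-wise error: 0.0486 for independent outcomes and 0.0337 at correlation 0.5. In no scenario did Holm lose a Bonferroni rejection.

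**The case against.** **Bonferroni is not wrong.** This stands. It is a valid, conservative procedure, and no conclusion reached under the SAP's rule would be invalid because of it. A reader might infer that the SAP contains a multiplicity error; the documents do not support that.

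**Bonferroni's extra conservatism buys something.** This also stands. The guaranteed family-wise bound is the same, but the realised error is lower under Bonferroni when some effects are real (0.021 against 0.030 with 12 of 24). Bonferroni also bounds the expected number of false rejections at 24 × 0.05/24 = 0.05, which Holm does not, and it has simple matching simultaneous confidence intervals. It would be too strong to say that the SAP gives up power for nothing.

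**The larger gains rest on favourable assumptions.** Largely accepted. The documents give no effect size, SD, correlation or arm sizes. The hypothesis names four broad domains, which is not evidence that 20 of 24 outcomes differ, and the safety outcomes at follow-up are exploratory rather than part of the tested family. The endpoints include counts, event rates and questionnaires, and second eyes may enter, so power figures from independent normal data may not carry over. The ordering of the two methods does not depend on any of this, but both need valid p-values.

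**Timing.** The SAP is written in the past tense and reports changes already made to the study. A reader might infer that results were known when it was written; the text does not establish this, but it is plausible. If so, replacing the stated rule with a more permissive one would be a post hoc change. This limits how Holm may be introduced and leaves the comparison between the methods unaffected.

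**Practical benefit.** Holm still starts at 0.002083 and gives the two primary endpoints no priority; a family of primaries alone would use 0.05/2 = 0.025. True, but that concerns the composition of the family, and Holm does not claim to settle it.

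**Conclusion.** The point holds as a low-cost improvement in efficiency. The SAP's threshold reproduces as single-step Bonferroni over 24 tests if alpha is 0.05, and neither document supplies a step-down rule. Holm on the same family never rejects fewer and keeps the same guaranteed family-wise bound. Those two statements are mathematical and need none of the assumed values.

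The size of the benefit does need them. At 1.2 SD it runs from a negligible 0.3 points with 2 real effects, through about 2 with 6 and 4 with 12, to about 10 with 20. A reader might conclude that genuine differences will be missed in this trial because of Bonferroni. The documents support only that this could happen, and that it is more likely the more outcomes truly differ.

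**What to change.** Replace the fixed cut-off in the SAP with wording such as: *Within the same family of primary and secondary tests, p-values are adjusted by Holm's step-down method; an outcome is significant if its adjusted p-value is below 0.05.* State the family-wise alpha and the number of tests, and report every adjusted p-value.

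If any comparative results are already known when the change is made, keep the Bonferroni result as the planned analysis and report the Holm result beside it, labelled post hoc. Every Bonferroni rejection will also appear under Holm, so the two can be shown in one table.

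The cost is one sentence in the SAP and one line of code, with no change to data collection, sample size or conduct. The downsides are that there is no single threshold to quote, matching simultaneous confidence intervals are less simple, and the realised family-wise error moves closer to 0.05 without exceeding it.
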